**Table JAIN.6.5. Seed Values for Multiple Imputation**

Analysis	Seed Value
Proportion of patients achieving IGA of 0 or 1 with a $\geq 2$ -point improvement from baseline at Week 16 and Week 24, with data up to rescue as the primary censoring rule.	123450
Percent change from baseline in EASI score at 16 weeks, with data up to rescue. EASI75 (at 16 weeks and at 24 weeks) and EASI90 (at 16 weeks).	123451
Proportion of patients achieving SCORAD75 at 16 weeks, with data up to rescue	123452
Proportions of patients achieving a 4-point improvement from baseline in Itch NRS at Week 16, with data up to rescue	123453
Mean change from baseline in Skin Pain NRS at Week 16, with data up to rescue	123454
Mean change from baseline in the score of Item 2 of the ADSS at Week 16, with data up to rescue	123455

Abbreviations: ADSS = Atopic Dermatitis Sleep Scale; EASI = Eczema Area and Severity Index score; EASI75 = 75% improvement from baseline in Eczema Area and Severity Index score; EASI90 = 90% improvement from baseline in Eczema Area and Severity Index score IGA = Investigator's Global Assessment for AD; NRS = Numeric Rating Scale; SCORAD75 = 75% decrease from baseline in Scoring Atopic Dermatitis values.

The final inference on treatment difference is conducted from the multiple datasets using Rubin's combining rules, as implemented in SAS® PROC MIANALYZE.

### 6.3.5. Tipping Point Analyses

To investigate the missing data mechanism, additional analyses using multiple imputation (MI) under the missing not at random assumption will be provided for the following primary and key secondary objectives:

- IGA (0,1) with  $\geq 2$ -point improvement at Week 16, baricitinib 4-mg + TCS or baricitinib 2-mg + TCS compared to placebo + TCS
- EASI percent change from baseline to Week 16, baricitinib 4-mg + TCS or baricitinib 2-mg + TCS compared to placebo + TCS
- Itch NRS 4-point improvement from baseline to Week 16, baricitinib 4-mg + TCS or baricitinib 2-mg + TCS compared to placebo + TCS

All patients in the ITT population will be included in the analyses. Data after the occurrence of intercurrent events (after application of the primary censoring rule) will be set to missing.

Within each analysis, a most extreme case will be considered, in which all missing data for patients randomized to baricitinib 1-mg, 2-mg, or 4-mg will be imputed using the worst possible result and all missing data for patients randomized to placebo will be imputed with the best possible result. Treatment differences will be analyzed using logistic regression or ANCOVA (Section 6.2.2.2) as appropriate.

For continuous variables, the following process will be used to determine the tipping point:

1. To handle intermittent missing visit data, a Markov chain Monte Carlo method (MCMC) (SAS® Proc MI with MCMC option) will be used to create a monotone missing pattern.
2. A set of Bayesian regressions (using SAS® Proc MI with MONOTONE option) will be used for the imputation of monotone dropouts. Starting from the first visit with at least 1 missing value, the regression models will be fit sequentially with treatment as a fixed effect and values from the previous visits as covariates.
3. A delta score is added to all imputed scores at the primary time point for patients in the baricitinib treatment groups, thus worsening the imputed value. The delta score is capped for patients based on the range of the outcome measure being analyzed.
4. Treatment differences between baricitinib and placebo are analyzed for each imputed dataset using ANCOVA (Section 6.2.2.2). Results across the imputed datasets are aggregated using SAS® Proc MI ANALYZE to compute a p-value for the treatment comparisons for the given delta value.
5. Steps 3 and 4 are repeated, and the delta value added to the imputed baricitinib scores is gradually increased. The tipping point is identified as the delta value which leads to a loss of statistical significance (aggregated p-value  $>0.05$ ) when evaluating baricitinib relative to the placebo group.

As a reference, for each delta value used in Steps 3 through 5, a fixed selection of delta values (ranging from slightly negative to slightly positive) will be added to imputed values in the placebo group, and Step 4 will be performed for the combination. This will result in a 2-dimensional table, with the columns representing the delta values added to the imputed placebo responses, and the rows representing the delta values added to the imputed baricitinib responses. Separate 2-dimensional tables will compare each baricitinib dose group to placebo.

A similar process will be used for the categorical variables:

1. Missing responses in the baricitinib groups will be imputed with a range of low response probabilities, including probabilities of 0, 0.1, and 0.2. These ranges may be changed after unblinding to provide the display of the observed data.
2. For missing responses in the placebo group, a range of response probabilities (for example, probability = 0, 0.05, ... 1) will be used to impute the missing values. Multiple imputed datasets will be generated for each response probability. These ranges may be changed after unblinding to provide the display of the observed data.

3. Treatment differences between baricitinib and placebo are analyzed for each imputed dataset using logistic regression (Section 6.2.2.2). Results across the imputed datasets are aggregated using SAS® Proc MIANALYZE to compute a p-value for the treatment comparisons for the given response probability. If the probability values do not allow for any variation between the multiple imputed datasets (for example, all missing responses in the placebo and baricitinib groups are imputed as responders and nonresponders, respectively), then the p-value from the single imputed dataset will be used.

The tipping point is identified as the response probability value within the placebo group that leads to a loss of statistical significance when evaluating baricitinib relative to placebo.

For tipping point analyses, the number of imputed datasets will be  $m=100$ . The seed values to start the pseudorandom number generator of SAS Proc MI (same values for MCMC option and for MONOTONE option) are given in [Table JAIN.6.4](#).

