### 4.2. Secondary Objectives

#### 4.2.1. Key Secondary Objectives

Key Secondary These are prespecified objectives that will be adjusted for multiplicity	
Objectives	Endpoints
To test the hypothesis that baricitinib 1-mg + TCS is superior to placebo + TCS in the treatment of patients with moderate-to-severe AD	
 
Proportion of patients achieving EASI75 at 16 weeks
 

To compare the efficacy of baricitinib 4-mg + TCS, baricitinib 2-mg + TCS, or baricitinib 1-mg + TCS to placebo + TCS in AD during the double-blind placebo-controlled treatment period as measured by improvement of signs and symptoms of AD	
 
Proportion of patients achieving IGA of 0 or 1 with a <math>\geq 2</math>-point improvement at 16 weeks
 
Proportion of patients achieving EASI90 at 16 weeks
 
Percent change from baseline in EASI score at 16 weeks
 
Proportion of patients achieving SCORAD75 at 16 weeks
 

To compare the efficacy of baricitinib 4-mg + TCS, baricitinib 2-mg + TCS, or baricitinib 1-mg + TCS to placebo + TCS in AD during the double-blind placebo-controlled treatment period as assessed by patient-reported outcome measures	
 
Proportion of patients achieving a 4-point improvement in Itch NRS at 16 weeks, 4 weeks, 2 weeks, and 1 week
 
Mean change from baseline in the score of Item 2 of the ADSS at 16 weeks and 1 week
 
Mean change from baseline in Skin Pain NRS at 16 weeks
 

To compare the efficacy of baricitinib 4-mg + TCS, baricitinib 2-mg + TCS, or baricitinib 1-mg + TCS to placebo + TCS in AD during the double-blind placebo-controlled treatment period as measured by improvement of signs and symptoms of AD	
 
Proportion of patients achieving IGA of 0 or 1 with a <math>\geq 2</math>-point improvement from baseline at 24 weeks
 
Proportion of patients achieving EASI75 at 24 weeks
 

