## 6. A Priori Statistical Methods

### 6.1. Determination of Sample Size

Study JAIN will aim to enroll 500 patients  $\geq 18$  years of age. Ignoring stratification, the proposed sample size will ensure  $>90\%$  power based on the Chi-square test to detect an absolute difference of approximately 25% between the 4-mg baricitinib and the placebo treatment group and the 2-mg baricitinib and placebo treatment group, each using a 2-sided alpha of 0.025 and assuming approximately 20% placebo response rate for the primary endpoint. These assumptions are based on what was observed in Phase 3 Study 14V-MC-JAIY.

Sample size and power estimates were obtained from nQuery® Advisor 7.0.

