**Table JAIN.6.4. Imputation Techniques for Various Variables**

Efficacy and Health Outcome Endpoints for 24-week interim analyses	Imputation Method
IGA (0,1), EASI75, 4-point Itch NRS improvement	NRI a,b , pMI a , Tipping point a
EASI90, SCORAD75	NRI a,b , pMI a
EASI percent change, ADSS Item 2 change, Skin Pain NRS change	MMRM a,b , mLOCF a , pMI a , mBOCF a
All remaining categorical measures	NRI a
All remaining continuous efficacy and health outcome measures	MMRM a , mLOCF a
Efficacy and Health Outcome Endpoints for 52-week interim analyses	
IGA (0,1), EASI75, 4-point Itch NRS improvement	NRI a,b
EASI90, SCORAD75	NRI b
IGA(0,1,2), EASI <=7, SCORAD <=25, DLQI <=5	NRI a,b
All remaining categorical measures	NRI b
EASI percent change, ADSS Item 2 change, Skin Pain NRS change	MMRM b , mLOCF b
All remaining continuous efficacy and health outcome measures	MMRM b , mLOCF b
Efficacy and Health Outcome Endpoints for Period 3 and/or Period 4 analyses	
IGA (0,1), EASI75, 4-point Itch NRS improvement	mLOCF c
All remaining categorical measures	mLOCF c
EASI percent change, ADSS Item 2 change, Skin Pain NRS change	mLOCF c
All remaining continuous efficacy and health outcome measures	mLOCF c

Abbreviations: ADSS = Atopic Dermatitis Sleep Scale; EASI = Eczema Area and Severity Index score; EASI75 = 75% improvement from baseline in Eczema Area and Severity Index score; EASI90 = 90% improvement from baseline in Eczema Area and Severity Index score; IGA = Investigator's Global Assessment for AD; mBOCF = modified baseline observation carried forward; mLOCF = modified last observation carried forward; MMRM = mixed model repeated measures; NRI = nonresponder imputation, NRS = Numeric Rating Scale; pMI = placebo multiple imputation; SCORAD75 = 75% decrease from baseline in Scoring Atopic Dermatitis values.

Notes: missing data related to COVID-19 may be imputed using the method specified in Section 6.3.7.

a Analyses utilizing the primary censoring rule.

b Analyses utilizing the secondary censoring rule.

c Analyses utilizing the Long-Term Extension Substudy censoring rule, or Long-Term Extension Non-responder censoring rule.

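### The tipping-point rule is not tied to the multiplicity procedure: it fixes p>0.05 for continuous endpoints and states no level for categorical ones, including the primary EASI75

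*SAP*

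**What the plan says.** SAP 6.3.5 offers tipping-point analyses for primary and key secondary objectives and describes two processes.

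- **Continuous.** The delta process opens with "For continuous variables, the following process will be used to determine the tipping point". Its last step reads "The tipping point is identified as the delta value which leads to a loss of statistical significance", and a bracket fixes this at an aggregated p-value above 0.05. The only continuous item in the section's list is "EASI percent change from baseline to Week 16, baricitinib 4-mg + TCS" (or 2-mg) against placebo. SAP 4.2.1 lists "Percent change from baseline in EASI score at 16 weeks" as a key secondary endpoint.
- **Categorical.** The process is introduced as similar and ends: "The tipping point is identified as the response probability value within the placebo group that leads to a loss of statistical significance". No p-value is attached.

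The bullet list in 6.3.5 omits EASI75, but a tipping-point analysis of it is planned elsewhere. Table JAIN.6.4 assigns one to "IGA (0,1), EASI75, 4-point Itch NRS improvement", Table JAIN.6.6 gives it a seed, and Table JAIN.6.8 lists it as a sensitivity analysis.

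On levels, SAP 6.1 plans the 4-mg and 2-mg primary comparisons "each using a 2-sided alpha of 0.025". SAP 6.4 controls the family-wise error at two-sided 0.05 over primary and key secondary endpoints through the graph in Figure JAIN.6.1. SAP 6.2 makes 0.05 the default and names the graphical strategy as an example of an exception. Section 6.3.5 does not mention the graph.

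**The concern.** A tipping-point analysis asks how far the missing-data assumption must be moved before a confirmatory conclusion is lost. That happens when p passes the level at which the hypothesis was rejected. If that level is below 0.05 and the cut-off is 0.05, the analysis answers an easier question: scenarios with p between the two levels are reported as still significant although the multiplicity-controlled claim has gone. The error has one direction, because the tipping point can only come out later or unchanged. It matters most for marginal results, where the tipping point is most likely to be read closely. For the categorical endpoints the difficulty is different: with no level stated, an analyst could carry over 0.05 from the preceding process or from the SAP 6.2 default.

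**Working it through.** **Inputs from the documents.** Placebo rate about 20% and difference about 25 points, so 45% v 20% (SAP 6.1). Two-sided alpha 0.025 per primary comparison (SAP 6.1). Planned arms: placebo 100, 4-mg 100, 2-mg 200 (protocol 5.1). Family-wise level 0.05 (SAP 6.4). The documents give no missing-data rate and no SD for EASI percent change, and the content of Figure JAIN.6.1 is not in the text available to me.

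**1. The plan's own figure.** Power = Φ[(d − z·SE0)/SE1], with SE0 pooled, SE1 unpooled and z = 2.241 for two-sided 0.025.
- 4-mg, 100 v 100: SE0 = √(0.325·0.675·0.02) = 0.0662; SE1 = √(0.0016 + 0.002475) = 0.0638. Power = Φ[(0.25 − 0.1485)/0.0638] = Φ(1.59) = 94.4%.
- 2-mg, 200 v 100: SE0 = 0.0590; SE1 = 0.0533. Power = Φ[(0.25 − 0.1323)/0.0533] = Φ(2.21) = 98.6%.

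Both exceed the stated 90%. The split 0.025 + 0.025 = 0.05 uses the whole family-wise level, so 0.025 is a coherent starting level for each primary comparison.

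**2. Continuous rule.** Let d be the treatment difference, SE its standard error (held fixed as a simplification) and f the fraction imputed on baricitinib. The difference is lost when (d − f·delta)/SE falls to the critical z, so delta = (d − z_crit·SE)/f. In the ratio of two tipping deltas f cancels. With z = d/SE,

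ratio = (z − 1.960)/(z − 2.241).

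| z of the main result | ratio | shift at 0.05 larger by |
|---|---|---|
| 4.5 | 2.540/2.259 | 12% |
| 4.0 | 2.040/1.759 | 16% |
| 3.2 | 1.240/0.959 | 29% |

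In absolute terms, assume a 20-point difference, SD 35, 20% missing and 100 v 100. Then SE = 35·√0.02 = 4.95. The tipping delta is (20 − 9.70)/0.2 = 51.5 points at 0.05 and (20 − 11.09)/0.2 = 44.5 at 0.025. Over SD 30 to 40 and both arm sizes, the 0.05 value is 9% to 22% larger.

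**3. Categorical rule, if 0.05 were used.** Placebo 20/100 after nonresponder imputation, uncorrected chi-square. The table gives the number of placebo patients who must become responders before p exceeds the threshold.

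| Active arm | at 0.05 | at 0.025 |
|---|---|---|
| 4-mg 45/100 (planned effect) | 12 | 10 |
| 4-mg 40/100 | 7 | 6 |
| 4-mg 35/100 | 3 | 1 |
| 2-mg 90/200 (planned effect) | 14 | 12 |
| 2-mg 80/200 | 9 | 7 |
| 2-mg 70/200 | 4 | 3 |

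**4. If local alpha is 0.05.** The two critical values coincide and the SAP rule is exact.

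**The case against.** The strongest reply is that the explicit 0.05 is not the primary endpoint's rule. It is the last step of the continuous process, and the primary is binary. A reader might put the 0.05 beside the 0.025 of SAP 6.1 and infer that the primary conclusion's robustness is being overstated. The documents do not support that: for EASI75 the level is unstated, and SAP 6.2 lets one read loss of significance as loss at the SAP 6.4 level. This stands, but it leaves the criterion for the primary endpoint undefined.

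Second, the correct alpha for EASI percent change depends on Figure JAIN.6.1. Alpha may have been recycled up to 0.05, so it cannot be said that the rule is certainly too lenient for that endpoint. This also stands, and it makes the overstatement conditional. It does not justify a fixed 0.05 either, since the local level may equally be 0.025 or lower.

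Third, the effect is modest for a strong result. At the planned effect z is 0.25/0.0662 ≈ 3.8 for 4-mg and 0.25/0.0590 ≈ 4.2 for 2-mg, and step 3 gives a gap of two patients for each. Other safeguards exist: placebo multiple imputation, the per-protocol and secondary-censoring analyses, a most-extreme case, and a two-dimensional delta table for continuous endpoints. These limit the consequence. They do not correct the cut-off that labels a scenario as significant.

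**Conclusion.** The point holds in a conditional form. SAP 6.3.5 fixes 0.05 for the continuous endpoint and no level for the categorical ones, and ties neither to the graph that decides those hypotheses. For any hypothesis tested below 0.05, a 0.05 rule gives a later tipping point than the confirmatory conclusion warrants. Where alpha has reached 0.05 there is no error.

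The size cannot be fixed from the documents. The illustration of about 12%, 16% and 29% at z of 4.5, 4.0 and 3.2 assumes a local alpha of 0.025 and a fixed standard error. It ignores the cap on delta and the planned combination of imputed datasets. The absolute shift also depends on the missing-data rate. The patient counts use a simple chi-square in place of the planned logistic regression.

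Sample size, the primary test and type I error control are untouched. This is a sensitivity-analysis criterion that should be corrected; it does not invalidate the confirmatory analysis.

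**What to change.** In SAP 6.3.5, replace the 0.05 criterion with one sentence that covers continuous and categorical endpoints alike: significance is lost when the aggregated p-value exceeds the local two-sided level at which that hypothesis was tested in the SAP 6.4 graph, which is 0.025 for each primary comparison unless alpha was propagated. Print the p-value in every cell of the tipping-point table, so that a reader can apply the relevant level directly. Add EASI75 to the list in 6.3.5 to match Tables JAIN.6.4, 6.6 and 6.8.

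The cost is a sentence and a table format, with no change to data collection, sample size or the primary test. The downside is that the reported tipping point may be somewhat less favourable. SAP 6.16 records that the Week 24 analysis has already been done. Where tables with p-values exist, they can be re-read at the local level without new imputations.

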**Table JAIN.6.6. Seed Values for Imputation**

Analysis	Seed Value
Proportion of patients achieving IGA of 0 or 1 with a $\geq 2$ -point improvement from baseline at Week 16 and at Week 24, with data up to rescue	123470
Percent change from baseline in EASI score at 16 weeks, with data up to rescue. EASI75 (at 16 weeks and at 24 weeks).	123471
Proportion of patients achieving a 4-point improvement from baseline in Itch NRS at Week 16, with data up to rescue	123472

Abbreviations: EASI = Eczema Area and Severity Index score; IGA = Investigator's Global Assessment for AD; NRS = Numeric Rating Scale.

### **6.3.6. Modified Baseline Observation Carried Forward**

A baseline observation analysis is performed by carrying forward the baseline assessment for the continuous measure. This assumes that the effect of treatments will be lost and patient status will return to the baseline after the occurrence of the intercurrent event (after application of the primary censoring rule). The mBOCF analyses will be applied to the ITT population where data from patients with non-missing baseline value will be included in the analyses.

### **6.3.7. Missingness due to COVID-19**

For missingness that COVID-19 is identified as the cause by the study team, the following imputation methods may be applied.

- For continuous measures, if missing due to COVID-19,
  - When they are analyzed using analysis of covariance (ANCOVA) for a single timepoint, modified last observation carried forward (mLOCF) method may be used (this is the same as missingness due to reasons other than COVID-19).
- For categorical variables, if missing due to COVID-19,

- mLOCF method may be used. This applies to categorical variables that are collected categorically, as well as categorical variables that are derived from measures that are collected as continuous, such as EASI50, EASI75 and EASI90.
  - This is on top of non-responder imputation specified in the sections above.
  - If a visit has missing data due to COVID-19 and the visit prior to this visit has missing data due to other reasons, mLOCF will be applied after the imputation for the prior visit is done.
- In addition, for IGA 0 or 1 and EASI75, multiple imputation (MI) method may be used. Seed = 123456 will be used for MI. Results from MIs will be aggregated to generate the final estimates for statistical inferences. This will be the main imputation method for these primary and key efficacy measures for visits with missing data due to COVID-19.
  - If a visit has missing data due to Covid-19 and the visit prior to this visit has missing data due to other reasons, MI will be applied after the imputation for the prior visit is done.

All measures collected through ePRO diary device should not be impacted by COVID-19. Therefore, no imputation method other than those specified before this section will be used.

For a specific DBL, if COVID-19 is still ongoing at the time of the DBL, the list of visits with missing data due to COVID-19 identified by the study for that lock may not be complete and may be updated in future locks. The imputation for missingness due to COVID-19 for each DBL is based on the list we receive for that specific lock.

For the planned locks to occur on and after July 2021, if the missing data due to COVID-19 does not exceed a prespecified 5% (Lin 2020) for each of the analysis population set, then there would no special imputation method applied.

## 6.4. Multiple Comparisons/Multiplicity

In **Period 2**, the primary and key secondary endpoints will be adjusted for multiplicity to control the overall family-wise Type I error rate at a 2-sided alpha level of 0.05. In **Period 3 or Period 4**, no adjustment for multiplicity will be performed.

For countries whose primary endpoint is IGA 0 or 1, a different graphical testing strategy will be described. The primary and key secondary endpoints will be adjusted for multiplicity to control the overall family-wise Type I error rate at a 2-sided alpha level of 0.05.

The following is a list of primary and key secondary endpoints to be tested.

Primary Null Hypotheses:

- Null Hypothesis[EASI75 W16]: Proportion of baricitinib 4-mg patients achieving EASI75 at Week 16 is equal to the proportion of placebo patients achieving EASI75 at Week 16.
- Null Hypothesis[EASI75 W16]: Proportion of baricitinib 2-mg patients achieving EASI75 at Week 16 is equal to the proportion of placebo patients achieving EASI75 at Week 16.

Key Secondary Null Hypotheses:

*Baricitinib 4 mg:*

- Null Hypothesis[IGA01 W16]: Proportion of baricitinib 4-mg patients achieving IGA of 0 or 1 with a  $\geq 2$ -point improvement from baseline is equal to the proportion of placebo patients achieving IGA of 0 or 1 with a  $\geq 2$ -point improvement from baseline at Week 16.
- Null Hypothesis[IGA01 W24]: Proportion of baricitinib 4-mg patients achieving IGA of 0 or 1 with a  $\geq 2$ -point improvement from baseline is equal to the proportion of placebo patients achieving IGA of 0 or 1 with a  $\geq 2$ -point improvement from baseline at Week 24.
- Null Hypothesis[EASI75 W24]: Proportion of baricitinib 4-mg patients achieving EASI75 is equal to the proportion of placebo patients achieving EASI75 at Week 24.
- Null Hypothesis[ITCH W16]: Proportion of baricitinib 4-mg patients achieving a 4-point improvement in Itch NRS is equal to the proportion of placebo patients achieving a 4-point improvement in Itch NRS at Week 16 among patients with baseline Itch NRS score  $\geq 4$ .
- Null Hypothesis[EASI PCFB]: Percent change from baseline in EASI score for baricitinib 4-mg patients is equal to the percent change from baseline in EASI score for placebo patients at Week 16.
- Null Hypothesis[ITCH W4]: Proportion of baricitinib 4-mg patients achieving a 4-point improvement in Itch NRS is equal to the proportion of placebo patients achieving a 4-point improvement in Itch NRS at Week 4 among patients with baseline Itch NRS score  $\geq 4$ .
- Null Hypothesis[SCORAD75]: Proportion of baricitinib 4-mg patients achieving SCORAD75 is equal to the proportion of placebo patients achieving SCORAD75 at Week 16.
- Null Hypothesis[EASI 90]: Proportion of baricitinib 4-mg patients achieving EASI90 is equal to the proportion of placebo patients achieving EASI90 at Week 16.
- Null Hypothesis[PAIN NRS]: Mean change from baseline in Skin Pain NRS for baricitinib 4-mg patients is equal to the mean change from baseline in Skin Pain NRS for placebo patients at Week 16.
- Null Hypothesis[ADSS2 W16]: Mean change from baseline in ADSS Item 2 score for baricitinib 4-mg patients is equal to the mean change from baseline in ADSS Item 2 score for placebo patients at Week 16.
- Null Hypothesis[ITCH W2]: Proportion of baricitinib 4-mg patients achieving a 4-point improvement in Itch NRS is equal to the proportion of placebo patients achieving a 4-point improvement in Itch NRS at Week 2 among patients with baseline Itch NRS score  $\geq 4$ .
- Null Hypothesis[ADSS2 W1]: Mean change from baseline ADSS Item 2 the score for baricitinib 4-mg patients is equal to the mean change from baseline in ADSS Item 2 score for placebo patients at Week 1.
- Null Hypothesis[ITCH W1]: Proportion of baricitinib 4-mg patients achieving a 4-point improvement in Itch NRS is equal to the proportion of placebo patients achieving a 4-point improvement in Itch NRS at Week 1 among patients with baseline Itch NRS score  $\geq 4$ .

*Baricitinib 2 mg:*

[figure not shown]
- Null Hypothesis[IGA01 W16]: Proportion of baricitinib 2-mg patients achieving IGA of 0 or 1 with a  $\geq 2$ -point improvement from baseline is equal to the proportion of placebo patients achieving IGA of 0 or 1 with a  $\geq 2$ -point improvement from baseline at Week 16.
- Null Hypothesis[IGA01 W24]: Proportion of baricitinib 2-mg patients achieving IGA of 0 or 1 with a  $\geq 2$ -point improvement from baseline is equal to the proportion of placebo patients achieving IGA of 0 or 1 with a  $\geq 2$ -point improvement from baseline at Week 24.
- Null Hypothesis[EASI75 W24]: Proportion of baricitinib 2-mg patients achieving EASI75 is equal to the proportion of placebo patients achieving EASI75 at Week 24.
- Null Hypothesis[ITCH W16]: Proportion of baricitinib 2-mg patients achieving a 4-point improvement in Itch NRS is equal to the proportion of placebo patients achieving a 4-point improvement in Itch NRS at Week 16 among patients with baseline Itch NRS score  $\geq 4$ .
- Null Hypothesis[EASI PCFB]: Percent change from baseline in EASI score for baricitinib 2-mg patients is equal to the percent change from baseline in EASI score for placebo patients at Week 16.
- Null Hypothesis[ITCH W4]: Proportion of baricitinib 2-mg patients achieving a 4-point improvement in Itch NRS is equal to the proportion of placebo patients achieving a 4-point improvement in Itch NRS at Week 4 among patients with baseline Itch NRS score  $\geq 4$ .
- Null Hypothesis[SCORAD75]: Proportion of baricitinib 2-mg patients achieving SCORAD75 is equal to the proportion of placebo patients achieving SCORAD75 at Week 16.
- Null Hypothesis[EASI90 W16]: Proportion of baricitinib 2-mg patients achieving EASI90 is equal to the proportion of placebo patients achieving EASI90 at Week 16.
- Null Hypothesis[PAIN NRS W16]: Mean change from baseline in Skin Pain NRS for baricitinib 2-mg patients is equal to the mean change from baseline in Skin Pain NRS for placebo patients at Week 16.
- Null Hypothesis[ADSS2 W16]: Mean change from baseline in ADSS Item 2 score for baricitinib 2-mg patients is equal to the mean change from baseline in ADSS Item 2 score for placebo patients at Week 16.
- Null Hypothesis[ITCH W2]: Proportion of baricitinib 2-mg patients achieving a 4-point improvement in Itch NRS is equal to the proportion of placebo patients achieving a 4-point improvement in Itch NRS at Week 2 among patients with baseline Itch NRS score  $\geq 4$ .
- Null Hypothesis[ADSS2 W1]: Mean change from baseline in ADSS Item 2 score for baricitinib 2-mg patients is equal to the mean change from baseline in ADSS Item 2 score for placebo patients at Week 1.
- Null Hypothesis[ITCH W1]: Proportion of baricitinib 2-mg patients achieving a 4-point improvement in Itch NRS is equal to the proportion of placebo patients achieving a 4-point improvement in Itch NRS at Week 1 among patients with baseline Itch NRS score  $\geq 4$ .

*Baricitinib 1 mg:*

- Null Hypothesis[IGA01 W16]: Proportion of baricitinib 1-mg patients achieving IGA of 0 or 1 with a  $\geq 2$ -point improvement from baseline is equal to the proportion of placebo patients achieving IGA of 0 or 1 with a  $\geq 2$ -point improvement from baseline at Week 16.

- Null Hypothesis[IGA01 W24]: Proportion of baricitinib 1-mg patients achieving IGA of 0 or 1 with a  $\geq 2$ -point improvement from baseline is equal to the proportion of placebo patients achieving IGA of 0 or 1 with a  $\geq 2$ -point improvement from baseline at Week 24.
- Null Hypothesis[EASI75 W16]: Proportion of baricitinib 1-mg patients achieving EASI75 is equal to the proportion of placebo patients achieving EASI75 at Week 16.
- Null Hypothesis[EASI75 W24]: Proportion of baricitinib 1-mg patients achieving EASI75 is equal to the proportion of placebo patients achieving EASI75 at Week 24.
- Null Hypothesis[ITCH W16]: Proportion of baricitinib 1-mg patients achieving a 4-point improvement in Itch NRS is equal to the proportion of placebo patients achieving a 4-point improvement in Itch NRS at Week 16 among patients with baseline Itch NRS score  $\geq 4$ .
- Null Hypothesis[EASI PCFB]: Percent change from baseline in EASI score for baricitinib 1-mg patients is equal to the percent change from baseline in EASI score for placebo patients at Week 16.
- Null Hypothesis[ITCH W4]: Proportion of baricitinib 1-mg patients achieving a 4-point improvement in Itch NRS is equal to proportion of placebo patients achieving a 4-point improvement in Itch NRS at Week 4 among patients with baseline Itch NRS score  $\geq 4$ .
- Null Hypothesis[SCORAD75 W16]: Proportion of baricitinib 1-mg patients achieving SCORAD75 is equal to proportion of placebo patients achieving SCORAD75 at Week 16.
- Null Hypothesis[EASI 90 W16]: Proportion of baricitinib 1-mg patients achieving EASI90 is equal to the proportion of placebo patients achieving EASI90 at Week 16.
- Null Hypothesis[PAIN NRS W16]: Mean change from baseline in Skin Pain NRS for baricitinib 1-mg patients is equal to the mean change from baseline in Skin Pain NRS for placebo patients at Week 16.
- Null Hypothesis[ADSS2 W16]: Mean change from baseline in ADSS Item 2 score for baricitinib 1-mg patients is equal to the mean change from baseline in ADSS Item 2 score for placebo patients at Week 16.
- Null Hypothesis[ITCH W2]: Proportion of baricitinib 1-mg patients achieving a 4-point improvement in Itch NRS is equal to the proportion of placebo patients achieving a 4-point improvement in Itch NRS at Week 2 among patients with baseline Itch NRS score  $\geq 4$ .
- Null Hypothesis[ADSS2 W1]: Mean change from baseline in ADSS Item 2 score for baricitinib 1-mg patients is equal to the mean change from baseline in ADSS Item 2 score for placebo patients at Week 1.
- Null Hypothesis[ITCH W1]: Proportion of baricitinib 1-mg patients achieving a 4-point improvement in Itch NRS is equal to the proportion of placebo patients achieving a 4-point improvement in Itch NRS at Week 1 among patients with baseline Itch NRS score  $\geq 4$ .

A multiple testing strategy for the primary and key secondary endpoints is implemented through a graphical testing scheme depicted in [Figure JAIN.6.1](#).

